Appendix C (The IRB-approved Protocol)

4.4 Multimedia Sampling Methods

Technicians for the Green Housing Study will visit homes during four visit periods (baseline, baseline part 2, 6-month follow-up, and 12-month follow-up). During each visit period, they will visit the home on Day 1 to collect samples/information and to deploy equipment, and return on Day 5 for sample and equipment collection. The EPA pilot study add-on will employ the same schedule to ensure that additional visits are unnecessary. Table 7 provides a timeline for the collection of additional information and samples to be collected for the EPA pilot study add-on during each visit period. The housing and community information, duplicate diet, toenail clippings, blood, and feces will only be collected at the baseline visit. The information/samples are listed in Table 7 in the order they are to be setup, discussed, or collected on a given visit day.

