Appendix C (The IRB-approved Protocol)

Table 7. Timeline for collection of field samples.

Information/Sample	Day 1	Day 2	Day 3	Day 4	Day 5
Indoor air – active	Setup				Collect
Indoor air – passive	Setup				Collect
Electrostatic dust collector (main play area, duplicate)	Setup				Collect
Surface dust by Swiffer					Collect
Questionnaire					Collect
Consumer product inventory	Collect				
Housing and community information ^a	Collect				
Surface wipes (kitchen & bathroom, n=8)	Collect				
Socks	Instructions ^b	Collect			Retrieve
Duplicate diet (n=9) ^{a,e}	Instructions ^b	Collect			Retrieve
GPS and accelerometer	Instructions ^b	Collect	Collect	Collect	Retrieve
Urine (toilet trained sibling) ^c	Instructions ^b		Collect	Collect	Retrieve
Urine-diaper (non-toilet trained sibling) ^c	Instructions ^b		Collect	Collect	Retrieve
Feces ^{a,e}	Instructions ^b		Collect		Retrieve
Toenail ^{a,e}	Collect				
Blood ^{a,d,e}	Collect				
Soil	Collect				
Household vacuum bag					Collect (if available)
Technician vacuum sample					Collect
Hand wipe					Collect

^aThese sample types will only be collected at the baseline visit.

^bInstructions will be given to the caregiver for the use/collection of socks, duplicate diet, GPS, accelerometer, urine (cup or diaper), and feces on Day 1. During Days 1-5, the caregiver will complete the associated tasks to allow for retrieval of these data, items, and samples on Day 5.

^cOnly one type of urine sample will be collected for the sibling, depending on whether they are toilet trained. Diapers collected must contain only urine. First morning voids will be collected for toilet trained children on 2 days; first morning voids or convenience samples will be collected for non-toilet trained children on 2 days.

^dSibling blood samples are optional.

^eDuplicate diet, feces, toenail clippings, and blood samples must be collected from the same participant (either the index child or sibling).

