Appendix C (The IRB-approved Protocol)

5.0 DATA ANALYSIS PLAN

Our analysis approach will enable us to evaluate the objectives described in Section 2.0. Study participants will be characterized with regard to demographic variables such as age and gender as well as activity-related metrics from questionnaires and electronic devices. Housing and product information will be characterized based on questionnaire responses and technician information collection. Statistical analyses will be completed for target analytes and survey information at each study time point, as well as comparisons between time points and renovated/non-renovated homes. All media will be analyzed and compared between and among each media type. Cross-sectional, longitudinal, and pre/post renovation analyses will be conducted. Data quality (e.g., percent completion or detected, accuracy, precision) will be assessed to help make decisions on more complex statistical analyses that can be conducted with the available data.

Descriptive statistics, univariate analyses, and correlations will be employed to evaluate the pilot study data collected in the third study site. Descriptive statistics will be developed for all variables to be used in data analyses addressing the research objectives. Categorical variables will be summarized by frequencies, while continuous variables will be summarized by mean, standard deviation, median, and range. Environmental and biological measurement variables such as analyte concentrations in dust and urinary biomarker concentrations will be characterized by mean and standard deviation, median, range, appropriate distribution percentile values, and percent of measurements above the detection limit.

For detection limit censored data distributions, appropriate approaches for reducing bias in distributional parameter estimates will be considered (substitution, maximum-likelihood estimation, or beta-substitution, depending on the degree of censoring and sample sizes). Measurement distributions will be assessed for normality using the Shapiro-Wilks or other appropriate normality test. Depending on the distribution, measurement values may be log-transformed to compute geometric means and geometric standard deviations. Other types of transformations and/or non-parametric analysis methods will be considered if necessary.

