Appendix C (The IRB-approved Protocol)

Objective	Measurements Required	Proposed Analysis Approach

5) Examine the relationships between consumer products in a residence, environmental concentrations, and exposure to active ingredients found in consumer product chemicals to support development and evaluation of models for predicting exposure to these chemicals
	
Household consumer product inventories, house dust, surface wipes, air, blood, urine concentrations
	
Quantification of relationships among media (dust, wipes, air) concentrations by chemical (correlations within and between subjects, descriptive statistics of ratio of air concentrations to surface concentrations); correlation between media (air and dust) concentrations and biomarker concentrations (within and between subjects by chemical); comparison of chemicals (individual or by class) in products found in the home with those found in dust and air (presence/absence) based on available databases of chemical ingredients; comparison of chemicals (individual or by class) in product categories reported as used in the home with those found in media (presence/absence, correlation of magnitude with reported use frequencies) based on available databases of chemical ingredients

6) Measure biomarkers of consumer product chemicals for young children in conjunction with environmental measurements to evaluate exposure and dose models
	
House dust, air, duplicate diet, blood, urine concentrations; activity information; survey information
	
Descriptive statistics; correlation analyses; uni- and multi-variate analyses for biomarker measurements; model runs (e.g., SHEDS, PBPK model, PROCEED) for forward/reverse dosimetry; comparison (t-test, correlations) between measurements and model predictions

7) Assess rapid, low burden, low cost methods for characterizing consumer product use in the residential environment to predict exposure to chemicals
	
Photographs of storage locations for household cleaning products and personal care products; barcode scanner inventory of products
	
EPA investigators will identify products in the photographs (blinded to scanner inventory). Image-based inventories will be evaluated against barcode-based inventories to assess collection accuracy (number of products correctly identified in photo divided by number in scanned inventory)

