Appendix C (The IRB-approved Protocol)

Objective 1: Identify and characterize factors affecting children's exposures to chemical ingredients from consumer products found in their everyday environment in order to support the data and modeling needs of the exposure components of EPA's national research programs

The data analysis goal for objective 1 is to identify predictive factors associated with children's exposures to chemical and biological contaminants in their residential environments, with a focus on consumer product chemicals. Exposure factors of interest include housing characteristics, human activity, consumer product presence/use, and environmental contaminant concentrations and distributions. Exposure factor assessment will inform development and evaluation of exposure models for children. Identification of predictive factors that differ between green and traditional housing may also enhance CDC's ability to examine asthma outcomes in the Green Housing Study. Data analyses for this objective will be integrated with those for other objectives (particularly objectives 2, 4, 5, and 8).

Descriptive and summary univariate statistics will be compiled for measurement and survey data to identify variables with sufficient measurable results and variability to consider in factor analysis. Spearman/Pearson correlation analyses will be performed within and between all measurement data to elucidate relationships and associations. Geometric mean and geometric standard deviations will be calculated for target analytes by sibling/age groups. T-tests and/or F-tests of differences between measurement distributions across sibling/age group and other categorical product, housing, and activity factors will be calculated. In some cases, factor assessment by survey and activity data categories may require non-parametric tests. Where there are sufficient data, regression model analysis with target analyte measurements as outcome variables and product, activity, location, and housing variables as potential exposure factors will be constructed to examine relative contributions to variability in children's exposures. A specific goal of the analysis is to determine how, and to what extent, child activity factors might influence relationships between environmental contaminant levels and exposures as measured from hand wipe, sock, and biomarker concentrations.

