Biomarker data can enhance exposure assessment through modeling in both a forward (exposure to dose) and reverse (dose to exposure) direction. Exposure and dose models such as NERL's SHEDS-Multimedia model and its variants use a probabilistic approach to predict the distribution of exposure and dose for a specified population. Inputs to the model include measurements (indoor air, house dust (preferential order: vacuum and surface wipe, socks, hand wipes)) and information collected from this study as primary inputs. These models use either a simple internal or a more complex PBPK model to predict the expected distribution of biomarker concentrations. The predicted distribution of concentrations will be compared (mean comparison by z-test, Chi-squared test for variance, ANOVA) with those measured to evaluate the use of such models and model parameters for young children.

Additionally, biomarker measurements will be analyzed in support of other study objectives. We will evaluate differences between case and control homes using ANOVA (objective 1). We will determine associations between a participant's biomarker concentrations before and after renovations using general linear and/or mixed models (objective 2). We will determine correlations between environmental and biomarker concentrations by chemical using Spearman and Pearson correlations (objective 5).

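### Objective 6 names ANOVA and a z-test for biomarkers with no unit of analysis or home term; on individual records, false positives would be about 9–12% per visit and 27–35% if visits are pooled (assumed correlation 0.3)

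*Protocol*

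**What the plan says.** Section 5.0, Objective 6, assigns methods question by question.

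- Between groups of homes: "We will evaluate differences between case and control homes using ANOVA (objective 1". Every enrolled home has an index child with asthma, so I read this as renovated against comparison homes.
- Measured against predicted biomarker distributions: "mean comparison by z-test, Chi-squared test for variance, ANOVA". Table 8 describes the same task differently: "comparison (t-test, correlations) between measurements and model predictions".
- A participant's biomarkers "before and after renovations using general linear and/or mixed models (objective 2". This is the only one of these three questions for which a method with a dependence term is named.

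The design produces repeated and clustered urine records. Homes are visited "during four visit periods (baseline, baseline part 2, 6-month follow-up, and 12-month follow-up". For the sibling, footnote c of Table 7 says: "First morning voids will be collected for toilet trained children on 2 days"; children in diapers also give samples on two days. Section 3.3.2 plans one sibling per family beside the index child, but anticipates that some households will have none. Section 4.4 restricts blood to the baseline visit.

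For Objective 1, Table 8 plans "regression model analysis with target analyte measurements as outcome variables and product, activity, location, and housing variables as potential exposure factors". Several of those factors belong to the home, not the child.

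**The concern.** The contrast of interest is between homes, but a biomarker record belongs to a child, a visit and a void. Records from one home share its sources, and the Objective 1 rationale in section 2.2 itself expects siblings' housing exposures to be alike. One-way ANOVA, or a z-test of the mean, applied to such records counts each as new information about the home. The standard error is then too small and differences between home groups appear by chance too often. In the model evaluation, a well-calibrated exposure model would too often seem to disagree with the measured mean.

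The before/after question, in the very next sentence, is allowed mixed models, and the sizing in section 2.3 includes a design effect of 2.0. Dependence is therefore recognised elsewhere but not carried into these two comparisons.

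**Working it through.** **The plan's own figure.** No error rate is stated for these tests. The add-on's one design figure is the minimum detectable limonene difference of 11.9 µg/m³ (section 2.3). Equation 1 in Appendix A, Part B, solved for the difference, is

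d = SD × √[D × 2(z_α + z_power)² × {1 + (n − 1)ρ} / (n × m)].

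With SD 19.4, D = 2.0, ρ = 0.3, m = 35, n = 3 and one-sided alpha 0.05:

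d = 19.4 × √[2 × 2 × (1.645 + 0.842)² × 1.6 / 105] = 11.9.

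Two-sided alpha gives 13.4. The figure is thus reproduced with n = 3 and one-sided alpha, neither of which section 2.3 states. In this formula 0.3 is the correlation among repeated observations, and clustering is the separate D. So 0.3 is not a stated within-home biomarker correlation, and its use below is an assumption.

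**Inputs for the check.** 32 homes per group (section 3.2); up to two children per home (3.3.2); four visits (4.4); one index-child urine sample per visit (Appendix A) and two sibling urine days per visit (Table 7).

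**Formula.** For k records per home with common correlation ρ, all treated as independent:

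design effect D = 1 + (k − 1)ρ; actual two-sided error = 2 × [1 − Φ(1.96/√D)].

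Example: k = 8, ρ = 0.3 gives D = 3.1, 1.96/√3.1 = 1.113, error 26.6%.

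| k | How it arises | D at 0.3 | Error at 0.3 | at 0.05 | at 0.5 |
|---|---|---|---|---|---|
| 2 | one visit, two children | 1.3 | 8.6% | 5.6% | 11.0% |
| 3 | one visit, both sibling voids | 1.6 | 12.1% | 6.2% | 16.6% |
| 4 | four visits, index child only | 1.9 | 15.5% | 6.8% | 21.5% |
| 8 | four visits, two children | 3.1 | 26.6% | 9.2% | 35.6% |
| 12 | four visits, both sibling voids | 4.3 | 34.5% | 11.5% | 44.2% |

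**Homes without a sibling.** Replace k by Σk²/Σk. If half the homes have a sibling, one visit gives (0.5×9 + 0.5×1)/(0.5×3 + 0.5×1) = 2.5, D = 1.45, error 10.4%. Four visits give (0.5×144 + 0.5×16)/(0.5×12 + 0.5×4) = 10, D = 3.7, error 30.8%. With the index child alone at one visit the error is 5.0%.

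**Simulation (8,000 runs, correlation 0.3).** Two-group ANOVA on records, 32 homes per group: 8.3%, 12.0%, 27.5% and 34.8% for k = 2, 3, 8 and 12. One-sample z-test, 64 homes, with the predicted mean and variance taken as known: 8.6%, 12.5%, 25.8% and 33.4%. The two-group test on home means: 4.9–5.2%.

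**The case against.** The strongest reply is that the protocol never says records are counted as independent. The between-home sentence speaks of homes and names no unit, and ANOVA on home means would hold its level. The same objective plans summaries for households as well as individuals. Unit of analysis and random effects are often left to a statistical analysis plan, which is not shown here. This stands as far as it goes: inflation follows only if the named tests are applied to individual records. But the text fits that use as well as any other, and it gives the between-home question the method without a dependence term.

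A reader might infer that the false-positive rate simply is 27–35%. The documents do not support that. It requires pooling all four visits, including the pre-renovation one, into one contrast, whereas section 5.0 says "Statistical analyses will be completed for target analytes and survey information at each study time point", with comparisons between time points added. It also needs a sibling in the home and the assumed 0.3, and it cannot apply to blood.

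Nor can the Objective 1 regressions be called wrong: no model form is stated for them.

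The consequences are also limited. Under Objective 5 the protocol doubts that population-level model comparisons will be useful at this sample size. Under Objective 6, large discrepancies lead to a search for gaps, not to formal rejection of a model. This lowers the stakes without making the named tests suitable for clustered records.

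**Conclusion.** The point holds in conditional form. For the between-home biomarker contrast and the measured-against-predicted comparison, the protocol names tests that need independent observations, in a design that yields clustered and repeated ones, and gives neither a unit nor a home term. On individual records a nominal 5% test would run at about 9–12% per visit, or 27–35% with all visits pooled, at an assumed within-home correlation of 0.3. Over 0.05 to 0.5 the ranges are about 6–17% and 9–44%.

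These figures assume one common correlation for every pair of records in a home. The per-visit 9–12% and the pooled 27–35% take every home to have a sibling. The point concerns contrasts between homes; comparisons of siblings within a home are a different matter. The change should be made, because the better method is cheap and Objective 1, to which the ANOVA is tied, is a primary objective.

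**What to change.** - Average the sibling's two voids per visit on the log scale.
- For between-home biomarker contrasts, replace plain ANOVA with a linear mixed model having random intercepts for home and for child within home, plus a visit term. Alternatively, analyse home means at a single time point.
- For the model evaluation, compare one geometric mean per child with its prediction, using standard errors clustered on home, in place of tests on pooled records. Reconcile the z-test in the Objective 6 text with the t-test in Table 8.
- Put the same home term in Objective 1 regressions on home-level factors whenever they use more than one record per home.

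The cost is a change of analysis wording and the use of standard software; no new data are needed. The downside is wider intervals and fewer nominally significant factors.

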Appendix C (The IRB-approved Protocol)

If samples sizes allow, the study participant data may be stratified (e.g., low/high concentrations, activity, age) to determine if the model can also predict differences between groups. If comparison of model predictions and measurements reveal large discrepancies, the Probabilistic Reverse dosimetry Estimating Exposure Distribution (PROCEED) tool can be used to reveal exposure, data, or model gaps that require additional consideration. As resources, time, and data suitability allow, we will explore relationships for biomarker measurements between blood and urine and compare biomarkers indicating stress (cortisol, cytokines) with multimedia measurements, health status, and exposure factors (personal, housing, community). These relationships will be investigated using methods such as analysis of variance (ANOVA) and principal component analysis (PCA).

Objective 7: Assess rapid, low burden, low cost methods for characterizing consumer product use in the residential environment to predict exposure to chemicals

The information collected in the consumer products inventory and use frequency sections of the questionnaire will be analyzed to address research questions related to children's exposures to chemicals. EPA staff will work in teams to identify the products in the inventory pictures. The product types will then be entered into an electronic database for further electronic processing and analysis. Data analysis will consist of (1) comparison of photo-based inventory to barcode-based inventory and (2) evaluation of consistency between repeated product usage frequency surveys. Additionally, the chemical ingredients can be used to inform the laboratory analyses of the multimedia measurements (objective 5).

Objective 8: Use low burden techniques and survey instruments to collect current information on children's activities, locations, and dietary habits to support exposure models and databases

The information collected in the EPA pilot study add-on questionnaire will be analyzed to develop mean and variability metrics of exposure factors for the children's cohorts being studied, and to identify interactions or correlations among exposure factors that could be used to derive relationships for future assessments of children.

Activity and location data will be aggregated into an electronic database and further processed by EPA investigators into a format consistent with EPA's Consolidated Human Activity Database (CHAD; McCurdy et al., 2000, U.S. EPA, 2002). This format includes demographic, date, and housing information linked with a minute-by-minute diary of location and activity for the individual studied. It is anticipated that if the data quality from the questionnaires are adequate, these time activity data (de-identified) would be permanently entered in CHAD for use by EPA exposure models (and available to the public via download).

Understanding the type, magnitude, and variability of time spent in microenvironments across ages, geographic region, subculture, or socioeconomic status is critical in performing exposure assessments for different populations of children. Therefore, time spent in each microenvironment by each child will be summarized by standard methods (for example, Xue et al., 2004). Of specific interest will be differences in time spent in locations for children of different ages in the same household. Additionally, location information will be combined with

Appendix C (The IRB-approved Protocol)

house dust loading measurements or personal samples in order to model children's soil and dust ingestion rates (objective 10). Finally, the interaction of time spent in different locations with housing and community factors such as crime rate, transportation options, and perception of children's safety will be quantified.

From the activity survey results, descriptive statistics of reported time spent in microenvironments and activities will be calculated. In addition, GPS-based time spent in microenvironments will be calculated using EPA's MicroTrac model (Breen et al., 2014). This model takes as input a GPS time-series and a general location of the participant's home and using a computational algorithm calculates time spent at home and in travel (in vehicles). The MicroTrac results will be compared with the survey results as in Breen et al. (2014). Differences among age groups, genders, and asthmatic/non-asthmatic children for both survey and GPS results will be quantified and tested using appropriate parametric or non-parametric techniques.

Children's activities are an important determinant of the types and amounts of chemicals encountered (McCurdy, 2000). Therefore, time spent in exposure-relevant activities (e.g., time spent with pet or exercising) will be characterized via standard methods (Xue et al., 2004). A primary analysis will evaluate age- and asthma-dependent differences in activity level in children living in the same household. The results from this analysis will aid in characterizing/elucidating the contributions of age, health, socioeconomic status, and other factors to describe the variability in activity levels. Similar to location, the interaction between housing and community factors (e.g., crime or noise pollution) and exposure relevant activities will be addressed. In addition, the location of high-dose rate activities (e.g., exercise) for these children will be compared to other, previously studied child cohorts to assess the influence of community or socioeconomic status-driven factors (such as distance from pollutant sources, or indoor versus outdoor exercise locations).

Exposure to chemical pollutants via dietary pathways is influenced by a large number of exposure factors related to food consumption habits. These exposure factors include habits or patterns related to: food types (food groups or agricultural commodities) (U.S. EPA, 2011b), food form such as fresh versus processed (Hamilton et al., 2004), home preparation of food (Melnik et al., 2011), organic versus conventional, and source of food (supermarket, home grown, etc.) (U.S. EPA, 2011b). Questionnaire results relevant to these factors will be analyzed, summarized, and potentially compared with data from existing studies (USDA, a, b) or other available data to identify unique exposure-relevant dietary factors for these children. In addition, exposure factors developed from these questions will also be used to inform the modeling of intake of soil and dust via contamination of food prepared in the home. Finally, the relationships between these exposure factors and relevant housing and community factors (e.g., restaurant density, distance to food retail outlets) may be assessed.

